4.3 Inclusion/Exclusion Criteria for Healthy Controls

Inclusion Criteria

Group 2: Healthy subjects without known psoriatic disease or cardiovascular disease

1. Age ≥ 18 & < 90
2. Able and willing to provide written informed consent for the study

Exclusion Criteria

2. Unable to speak Spanish or English
3. Active smoking (within the past year)
4. Autoimmune, rheumatologic or inflammatory disease which are not psoriasis or psoriatic arthritis
5. Known active cancer receiving treatment
6. Pregnancy
7. Anemia (hemoglobin < 9 mg/dl) or thrombocytopenia (Platelet count < 75), or thrombocytosis (Platelet count > 600)
8. A history of severe bleeding or bleeding disorders
9. Current medication use which interact with either aspirin or atorvastatin
10. Chronic kidney disease (CrCl < 30 ml/min)
11. Congestive heart failure
12. Currently taking aspirin or a statin.
13. NSAID use within the past 48 hours

Recruitment goals are listed in the schedule of assessments below. Both female and males will be recruited. Patients will be recruited from the outpatient general medicine, musculoskeletal/rheumatology and dermatology clinics at the NYU Faculty Group Practice (FGP) clinics including the Psoriasis, psoriatic arthritis ambulatory clinic, psoriasis and dermatology ambulatory care center and Bellevue Hospital Adult Clinics. We will also recruit from the Hospital for Joint Disease Psoriatic arthritis clinic which is staffed by NYU faculty. Patients fulfilling inclusion and exclusion criteria will be identified by their health care professional, who will obtain verbal consent for contact by a member of the research staff. Study brochures will also be left at the front desk of these practices in the event that subjects would like more information from study staff. Patients will be approached after their visit with the health care provider in the clinic setting. Subjects and healthy controls will also be recruited from posted fliers across the medical center. Additionally, subjects who have previously enrolled in any study (10-00607, S12-03123, S14-00531, s14-01418) by the co - PI ([name]) and who checked off the box that they may be contacted by a member of the study staff for potential enrollment will be included.

Additional recruitment will be done through posted fliers and approved brochures at private dermatology offices with dermatology office staff permission. We will also recruit through social media postings including Craigslist, Facebook, psoriatic support groups and national psoriatic society patient

advocacy groups as well the NYU approved research match. The advertisement for these postings will contain the same content as noted on the IRB approved flyer. This social media advertisement will also include the health-union psoriasis advocacy website.

Working with MCIT and DataCore we will be using *Epic's Reporting Workbench tool* to identify potential subjects that have psoriasis and present to the dermatology FGP, arthritis or phototherapy clinics. We will screen these subjects and then if they meet study inclusion criteria and has agreed to be contacted for potential studies then they will be contacted. *Contact will be initiated using Epic and the patient portal, MyChart, via Epic's Research Recruitment functionality. The information used to send the MyChart message will be the same as that used for other study advertisements.*

Only subjects that have the capacity to consent will be asked to consent.

Vulnerable Population

We will not be enrolling any vulnerable populations.

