The mechanism(s) between psoriatic disease and CVD are still being characterized.⁷ The systemic inflammation is linked to the production of numerous inflammatory cytokines such as interferon – γ , tumor necrosis factor (TNF), IL-17 and IL-22 with an overall activation of the innate immune system response.⁸ Through systemic inflammation, the initial stages of atherosclerosis develop with upregulation of vascular endothelial adhesion molecules and leukocyte translocation, platelet activation and increased vessel wall permeability to lipoproteins and inflammatory mediators.⁹

There have been studies linking the earliest phases of atherosclerosis, endothelial dysfunction and psoriasis. Psoriatic patients have impaired flow-mediated dilation, increased arterial stiffness and increased carotid intima-media thickness.¹⁰ Biochemically, a variety of extracellular microparticles, involved in both endothelial cell and platelet activation are elevated in those with moderate to severe psoriasis.¹¹ Platelet activation in particular through measurement of platelet-derived microparticles and soluble P-selectin are increased in psoriasis and linked to psoriasis severity.¹²

While there have been studies evaluating the effects of psoriatic specific treatment on endothelial dysfunction, there is a lack of evidence on the use of medications typically used for the primary prevention of CVD within the psoriatic population.¹⁰ The goals of the proposed study are three fold: As a first step to assess endothelial dysfunction, we will assess vascular function in psoriasis patients through non-invasive ultrasound imaging and through a novel technique: direct analysis of endothelial cells with minimally invasive endothelial vein harvesting.¹³ As a second goal, we will assess thrombotic risk through platelet activation and platelet – endothelial interaction. Finally, as a third goal, we will assess in patients with moderate to severe psoriatic disease changes to the endothelial function and platelet activation over time with the use of 81mg of aspirin and/or 40mg of atorvastatin.

3. Specific Aims

- 3.1 To evaluate the association between moderate to severe psoriatic disease and measures of vascular function.
- 3.2 To evaluate the association between moderate to severe psoriatic disease and measures of thrombotic risk.

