4.1 Recruitment

We will recruit patients across the spectrum of psoriatic disease (includes psoriasis and psoriatic arthritis and age and sex matched health controls).

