4.2 Inclusion/Exclusion Criteria for Psoriatic Patients

Inclusion Criteria

1. Group 1: Subjects with a history of moderate to severe psoriatic disease
2. Age ≥ 18 & < 90
3. Able and willing to provide written informed consent for the study

Exclusion Criteria

1. Unable to speak Spanish or English
2. Active smoking (within the past year)
3. Autoimmune, rheumatologic or inflammatory disease which are not psoriasis or psoriatic arthritis
4. Known active cancer receiving treatment
5. Pregnancy
6. Anemia (hemoglobin < 9 mg/dl) or thrombocytopenia (Platelet count < 75), or thrombocytosis (Platelet count > 600)
7. A history of severe bleeding or bleeding disorders
8. Current medication use which interact with either aspirin or atorvastatin
9. Chronic kidney disease (CrCl < 30 ml/min)
10. Congestive heart failure
11. Currently taking aspirin or a statin.
12. NSAID use within the past 48 hours

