10. DATA ANALYSIS

All eligible subjects will be assigned a unique identification number upon enrollment in the study. Initial study data will be recorded on a printed form, which will be later converted to electronic database (Redcap). All potential identifiers will be kept separately in a safe location by the PI in a locked file cabinet in a locked room. After verification of entered data at completion of the study all potential identifiers will be stripped from the database.

a. Aim 1

To evaluate the association between moderate to severe psoriatic disease and measures of vascular function. Brachial artery reactivity will be modeled as a continuous variable in all analyses. Multiple linear regression will be used to estimate the difference in brachial artery reactivity between those with psoriasis and age and sex matched controls. Conventional adjustment for age and sex will be entered first into the model. Additional multivariable adjustment for other relevant covariates (e.g., body mass index, hypertension, renal function, LDL cholesterol) will then be performed.

A similar analysis plan will be undertaken for central pulse pressure (CPP) and pulse wave velocity (PWV) which will be modeled as continuous variables in all analyses. Multiple linear regression will be used to estimate the difference in CPP and PWV between those with psoriasis and age and sex matched controls. Conventional adjustment for age and sex will be entered first into the model. Additional multivariable adjustment for other relevant covariates (e.g., body mass index, hypertension, renal function, and LDL cholesterol) will then be performed.

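### Known cardiovascular disease is barred in controls but not in Group 1, which can bias the Aim 1 and Aim 2 comparisons by a modest amount that the documents do not let one fix

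*Combined protocol and SAP*

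**What the plan says.** Section 4.3 defines Group 2 as "Healthy subjects without known psoriatic disease or cardiovascular disease". Section 4.2 defines the cases as "Subjects with a history of moderate to severe psoriatic disease", with age and consent conditions and nothing on freedom from CVD.

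The Group 1 exclusions that touch on CVD are "Congestive heart failure", "Currently taking aspirin or a statin" and use of drugs that interact with either study drug. Smoking within the past year and a creatinine clearance below 30 ml/min are also barred. Section 4.3 repeats all of these for controls, so none of them explains or offsets the extra condition placed on controls.

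Section 4.1 speaks of "age and sex matched health controls". For Aim 1, section 10 enters age and sex first and then states: "Additional multivariable adjustment for other relevant covariates (e.g., body mass index, hypertension, renal function, LDL cholesterol) will then be performed". For Aim 2 it refers to other covariates without naming any, and adds model selection. Section 4.4 provides a subject history form covering the complete medical history, and a baseline interview that reviews clinical history.

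**The concern.** A psoriatic patient with known coronary, cerebrovascular or peripheral arterial disease who takes neither aspirin nor a statin, and meets the other criteria, can enter Group 1. The same history bars a control. If such patients have worse vascular function, part of the case-control difference in Aim 1 reflects established CVD in a few cases and not psoriatic disease.

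The asymmetry also sits badly with the study's own question. The title concerns subclinical CVD, and section 2 motivates the work by saying that "there is a lack of evidence on the use of medications typically used for the primary prevention of CVD within the psoriatic population". Section 1 states that psoriatic patients have more atherosclerotic heart disease and infarction than matched controls, so the gap lies in the group where known CVD is more likely. What is at stake is mainly the estimate: section 9 wants this pilot's cross-sectional trends to support further study proposals.

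**Working it through.** **The plan's own figure.** Section 9 gives more than 90% power for the baseline NF-kB comparison with 40 cases, 10 controls, d = 1.2 and alpha 0.05. A two-sample t test (noncentral t, 48 degrees of freedom) gives 91.4% two-sided and 95.6% one-sided, so the figure reproduces. The imaging figure (more than 80% power for a 35% difference) cannot be fully reproduced, because no SD is given. With 40 against 10, 80% two-sided power needs d of at least 1.01.

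**Bias formula.** Let f be the share of Group 1 with known CVD, and g the shift in outcome, in SD units and in the adverse direction, that goes with it. The share among controls is zero by design. The unadjusted difference then moves by f × g. Neither f nor g is in the documents. I take f from 2.5% to 20% (1 to 8 of 40 cases) and g from 0.5 to 1.5 SD as assumptions.

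| f | cases of 40 | bias, g = 0.5 | bias, g = 1.0 | bias, g = 1.5 | false-positive rate at g = 0.5 / 1.0 / 1.5 |
|---|---|---|---|---|---|
| 2.5% | 1 | 0.0125 SD | 0.025 SD | 0.0375 SD | 0.050 / 0.050 / 0.046 |
| 5% | 2 | 0.025 SD | 0.05 SD | 0.075 SD | 0.051 / 0.048 / 0.047 |
| 10% | 4 | 0.05 SD | 0.10 SD | 0.15 SD | 0.053 / 0.053 / 0.054 |
| 20% | 8 | 0.10 SD | 0.20 SD | 0.30 SD | 0.055 / 0.072 / 0.088 |

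The last column is simulated with no true psoriasis effect and a two-sided t test at 0.05, using 40,000 runs per setting.

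**Scale.**
- Against the smallest difference detectable with 80% power, the bias runs from 0.0125/1.01 = 1% to 0.30/1.01 = 30%.
- The standard error of the difference is √(1/40 + 1/10) = 0.354 SD, so even the largest bias in the table is 0.30/0.354 = 0.85 of a standard error.
- For CVD alone to produce a 1.01 SD difference, f would have to be 1.01/1.5 = 67% at g = 1.5 and essentially all cases at g = 1.0. At g = 0.5 it is impossible.

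**In FMD points.** Assume that the 35% is taken of the laboratory mean of 5.89% in section 4.5.3. The target is then 0.35 × 5.89 = 2.06 points, and the stated power implies an SD of at most 2.06/1.01 = 2.04. At that ceiling the bias is 0.0125 × 2.04 = 0.03 to 0.30 × 2.04 = 0.61 points.

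**What a covariate would do.** Suppose a known-CVD indicator is added to a model with the group term alone. The indicator is estimable within Group 1, and the group coefficient becomes the mean of CVD-free cases minus the mean of controls. That is the same contrast as restricting Group 1 to patients without known CVD. With further covariates the two routes can differ slightly, because patients with CVD still contribute to the other slopes.

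**The case against.** The strongest case against the point has four parts.

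- **The affected group is probably small.** Barring heart failure, aspirin and statin users, interacting drugs, poor renal function and recent smokers should remove many patients with known CVD. This stands, and is why the range for f starts at one patient in 40. It lowers the share but does not make it zero.
- **The Aim 1 covariates are only examples.** CVD history is collected and could be added as a relevant covariate. This stands too: CVD is unnamed, not ruled out. But nothing commits the analysis to it, and Aim 2 leaves its covariates to model selection.
- **CVD may lie on the causal pathway.** Aims 3.1 and 3.2 ask about association, and CVD caused by psoriatic disease could count as part of it. But a total association would require controls to carry their natural burden of CVD, and a subclinical one would remove CVD from both groups. Screening only the controls gives neither.
- **The test is barely affected.** The false-positive rate stays between 0.046 and 0.054 for f up to 10%. This stands; the harm is chiefly to the estimate.

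A reader might infer three stronger things that the documents do not support. One is that regression could not repair the comparison because no control can have CVD; the working shows that an indicator does so in a simple model. Another is that the bias always favours the study hypothesis. It is zero if no such patient enrols, and in Aim 2 cases with known CVD may take other drugs that lower platelet activity. The last is that Aim 3 is affected. Section 4.5.2 confines that component to Group 1, so the eligibility difference does not enter, and section 10 specifies paired t tests within patients.

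**Conclusion.** The asymmetry is real and the documents give no reason for it: known CVD other than the types barred in both groups can occur only among cases. It can bias the Aim 1 difference, probably away from zero, provided affected patients have worse vascular function. For Aim 2 a bias is possible but its direction is less certain.

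Under the assumed ranges (2.5% to 20% of cases, 0.5 to 1.5 SD) the bias is about 0.01 to 0.30 SD. That is modest beside the 1.01 SD detectable with 80% power and smaller than one standard error. It would not by itself create a positive finding of the planned size. The point is worth acting on because the bias would be built into the design, and it can be removed cheaply.

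**What to change.** Make the two groups comparable on known CVD, using one written definition for both.

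- **If enrolment allows:** add to section 4.2 the no-known-CVD condition that section 4.3 already applies.
- **If patients are already enrolled:** add a sentence to section 10 that bases the main Aim 1 and Aim 2 comparison on Group 1 members without known CVD, identified from the subject history form and baseline interview. A prespecified known-CVD indicator, kept in the model whatever the selection procedure does, is an equivalent route in a simple model.
- **Where patients with known CVD have been enrolled:** report the all-patients result alongside, with the number of cases affected.

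The cost is one eligibility line or one analysis-set sentence, with no new data collection, and a few cases lost from the comparison. Because the 10 controls dominate the standard error, precision hardly suffers: losing 8 of 40 cases raises it from √(1/40 + 1/10) = 0.354 SD to √(1/32 + 1/10) = 0.362 SD, about 2.5%.

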4.4 Informed consent

If a subject wishes to participate, a member of the research team will review the informed consent documents, answer any questions, and obtain written consent for participation in the study and obtain written consent for future analysis, contact, and sample storage. Subjects will be given a "Subject history form" to fill out asking for a complete medical history. They will also be given an appointment reminder sheet to bring with their consent form. They will bring the subject history form to their first baseline assessment appointment. Participants will consent to complete the baseline assessments (see table 1). Participants may opt to decline participation in any baseline assessment they feel uncomfortable with or time constraints do not allow. Follow-up assessments will be completed in those who agree to aspirin or atorvastatin usage for the longitudinal part of the analysis. Participation in follow-up assessment is not required for participation in the baseline assessment. The consent process will take place in private offices at the NYU FGP, CTSI, ambulatory care center, Seligman Center for Advanced Therapeutics and Bellevue adult clinics. Subjects will be given the opportunity to be contacted for future studies that they may qualify for as well. A member of the research team will conduct the baseline interview with the subject and review the clinical history, demographic information and medication use with the individual. All information including the consent will be kept under double lock and key at the PI's office in NYU Skirball 9th floor.

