4.5.2 Longitudinal component (Group 1 only)

After baseline assessment, those with moderate to severe psoriatic disease will be offered by the study physician randomly the opportunity for longitudinal follow up and to take either aspirin and/or atorvastatin. For 2 weeks +/- 4 days, 1/4th of the subjects enrolled will be offered 81mg of aspirin, 1/4th of the subjects enrolled will be offered atorvastatin 40mg, ¼ will be offered both aspirin and atorvastatin and 1/4th will be offered nothing. Participants will be given the opportunity to only participate in the baseline assessment and opt out of the opportunity to take aspirin and/or atorvastatin and longitudinal component.

Both aspirin and atorvastatin are routinely used and approved in medical practice for the primary prevention of coronary artery disease. These medications are frequently used in the psoriatic population based on national guidelines when a calculated cardiac risk score is elevated (considered at moderate to high risk of cardiovascular events). These medications will be obtained from the Tisch outpatient pharmacy. They will be stored and dispensed with CTSI oversight. A drug accountability and storage log will be kept as per NYU research protocol.

A follow up assessment will be planed (table 1) at 2 weeks +/- 4 days and will include repeat blood draw (60 ccs, for the use of platelet function testing, biospecimen collection) and repeated endothelial vein harvesting. The end of the study is considered when the subject completes the follow up assessment. All study drugs will be stopped at this time. If the subject wishes to continue the study drugs they will be referred to their primary medical provider for further management.

A subject will be able to opt out of any part of the follow up assessment they desire. If a subject agrees to be started on aspirin and/or atorvastatin for the longitudinal part of the analysis and therapy for psoriasis is planned by the referring provider, we will attempt to perform the longitudinal follow up prior to their starting medication. Participation in this study will not impact planned treatment of the subjects by their primary provider.

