All subjects may be asked to provide additional information about their medical history, update any interim history and provide additional samples as noted above. Health information will be monitored overtime by review of the medical chart. Additional questions may be asked by phone or during routine clinical follow-up, as appropriate.

Table 1. Patient Group		Baseline	Longitudinal Analysis	Follow-up
1 n = 40	Moderate to severe psoriatic disease	1) Blood 2) Endothelial vein harvesting 3) Vascular function imaging	Offered: 1) Aspirin 2) Atorvastatin	1) Blood 2) Endothelial vein harvesting 3) Additional medical history

				obtained
2 n = 10	Healthy Controls	1) Blood 2) Endothelial vein sampling 3) Vascular function imaging		1) Additional medical history obtained

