4.5.6 Longitudinal Follow Up Data Collection

Participants enrolled in the longitudinal part of this study will be offered the option to participate in follow-up biospecimen collection. This follow-up will allow us to assess how aspirin and/or atorvastatin affect platelet and endothelial function and inflammation. This follow-up component will consist of additional blood samples of ≈ 30ml (2 tablespoons or less) that will be collected for different measurements of platelet function, lipid levels, coagulation, inflammation, and approximately 30 ccs of blood will be used for isolation of RNA, microRNA and storage of DNA at -80C. The samples will be stored in the PI's lab at the NYU Science building 7th floor without any identifying information other than a code number. Repeat endothelial vein harvesting will also be performed as described above.

Overall, code numbers used for collection of samples will not be based on any information that could be used to identify the subject (for example, social security number, initials or birth date). The master list linking names to code numbers will be kept in a locked file cabinet, separate from all research information.

If participating in the optional follow-up collection, the total amount of blood withdrawn (baseline plus follow up) will be no more than 120 ml (approximately 7 tablespoons and 1/4 for a standard blood donation). This amount of blood collection is within established safety guidelines of research blood collection in adults. Blood collection at baseline and at the follow up time points will allow us to examine how the treatment of aspirin and atorvastatin modify 1) endothelial vein function in psoriatic disease, 2) changes to platelet activity and 3) alterations in coagulation and inflammation in those with psoriatic disease.

For all cases and controls, we will call 1 week after each procedure to assess how patients are feeling after endothelial vein harvesting. Adverse events will be managed as mentioned below.

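### Section 4.4 conflicts with section 4.5.2 and Table 1 on whether the untreated quarter of Group 1 is measured at week 2

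*Combined protocol and SAP*

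**What the plan says.** The places that bear on who is measured at week 2 are these.

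- **Section 4.4 (Informed consent):** "Follow-up assessments will be completed in those who agree to aspirin or atorvastatin usage for the longitudinal part of the analysis".
- **Section 4.5.2, the offer:** Group 1 patients are offered "randomly the opportunity for longitudinal follow up and to take either aspirin and/or atorvastatin". Two quarters are offered one drug each; of the rest, "¼ will be offered both aspirin and atorvastatin and 1/4th will be offered nothing".
- **Section 4.5.2, the visit:** "A follow up assessment will be planed (table 1) at 2 weeks +/- 4 days". It comprises a repeat blood draw and a repeat harvest, and no drug condition is attached. The same section lets participants stop at baseline or skip any part of follow-up.
- **Table 1, Group 1 row (n = 40):** the follow-up cell reads "1) Blood 2) Endothelial vein harvesting 3) Additional medical history" and is not split by arm. The longitudinal cell reads "Offered: 1) Aspirin 2) Atorvastatin".
- **Table 1, healthy controls:** medical history only at follow-up.
- **Section 4.5.6:** "Participants enrolled in the longitudinal part of this study will be offered the option to participate in follow-up biospecimen collection". The stated purpose is: "This follow-up will allow us to assess how aspirin and/or atorvastatin affect platelet and endothelial function and inflammation".
- **Section 11.5:** a week-2 visit for the longitudinal cohort, which is not defined by arm.
- **Section 10, Aim 3:** paired t-tests for the three drug regimens. The untreated quarter is not named.

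**The concern.** Section 4.4 is the one sentence that says who completes follow-up, and it makes agreement to a drug the condition. Patients allocated to nothing cannot meet it. A coordinator working from 4.4 would not book their week-2 visit; one working from Table 1 would.

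The untreated quarter is the only group of psoriatic patients that could show what two weeks, a previous harvest and a repeat visit do without a study drug. Healthy controls cannot stand in, because they have no week-2 samples. Visit-to-visit variation is a real issue in this laboratory's own data: section 4.5.3 gives a day-to-day coefficient of variance of 15-30% for FMD, with a reliability coefficient of 46%. FMD is not among the week-2 measurements in Table 1, and no such figure is given for the harvest or platelet measures, so this is an indication and not an estimate for the Aim 3 outcomes.

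A missing between-arm test can be added when the data are analysed. Missing week-2 samples cannot.

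**Working it through.** **1. The passages side by side**

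| Place | Drug condition for week 2? | Untreated quarter |
|---|---|---|
| 4.4 | Yes, agreement to a drug | Left out if read literally |
| 4.5.2, offer | Follow-up and drug offered together | Unclear |
| 4.5.2, week-2 visit | None | Covered as part of Group 1 |
| Table 1, follow-up cell | None, n = 40 | Covered |
| 4.5.6 and 11.5 | Membership of the longitudinal part or cohort | Not stated |

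No passage says outright that the untreated quarter returns, and none says outright that it does not.

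**2. How many patients depend on the answer**

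Inputs: 40 in Group 1 (Table 1) and four equal offers (4.5.2). Untreated quarter: 40 × 1/4 = 10.

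- Under 4.4: 0 of 10 untreated patients sampled, and at most 3 × 10 = 30 week-2 samples in all.
- Under Table 1: at most 10 of 10, and at most 40 in all.

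The upper figures are ceilings, because opt-out is allowed and no rate is given.

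**3. Does the stated power show which was intended?**

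Section 9 gives 74% power with n = 10 per group, d = 0.8 and alpha 0.05, for a difference between groups. Sidedness and the type of d are not stated. Noncentral-t power:

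- Paired test in one arm: noncentrality 0.8 × √10 = 2.53 on 9 df. Power is 75.4% one-sided and 61.6% two-sided. A one-sided signed-rank test, using its asymptotic efficiency 3/π, gives 73.4%.
- Two arms of 10, with d on the SD of change: noncentrality 0.8 × √(10 × 10/20) = 1.79 on 18 df. Power is 53.0% one-sided and 39.5% two-sided.

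The 74% is close to a one-sided within-arm test and far from a comparison of two arms of 10. It is not a unique match: a three-group repeated-measures interaction with f = 0.4 and zero correlation gives 74.9%. None of the close matches needs an untreated arm, so the figure does not settle the conflict.

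**4. What is lost if the arm is not measured**

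- Lost: aspirin versus nothing, atorvastatin versus nothing, both versus nothing, and the full two-by-two margins. A margin compares 20 with 20: noncentrality 0.8 × √(20 × 20/40) = 2.53 on 38 df, power 69.3% two-sided.
- Kept: both versus atorvastatin alone (aspirin on a statin background) and both versus aspirin alone (atorvastatin on an aspirin background). Each is 10 v 10, 39.5% two-sided at the same d.

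**5. What an uncontrolled pre/post test does with drift (illustration)**

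Assume no drug effect and a common shift of δ SDs of change, tested by a two-sided paired t-test with n = 10, so that the noncentrality is δ√10.

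- δ = 0.2: noncentrality 0.63, significant 8.8% of the time.
- δ = 0.5: noncentrality 1.58, significant 29.3% of the time.

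The nominal rate is 5%. The range of δ is an assumption; the documents give no drift figure.

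**The case against.** A reader might infer from 4.4 that the untreated quarter certainly has no week-2 blood or harvest. The documents do not support that. The sentence contains no word such as only, and it stands in the consent section beside text explaining that follow-up is optional. The scheduling text is 4.5.2 and Table 1, which set no drug condition. The two-week period in 4.5.2 also introduces all four offers, which would have little point for a quarter that is not followed.

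Nor does Table 1's longitudinal column prove exclusion. It omits the no-drug arm, but it lists drugs rather than arms and does not show the combination arm separately either. The purpose sentence in 4.5.6 says why follow-up is done, not who receives it.

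A reader might also infer that without the untreated arm no analysis could separate drug from visit effects and that the random offer would serve no purpose. That goes too far. Combination versus single-drug contrasts would still remove a shift common to the arms compared.

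Finally, this is a self-described pilot. That excuses low power, but it does not excuse leaving open whether an allocated arm is measured. What stands of the objection is that the fault is a contradiction, not a settled omission, and that the loss under 4.4 is specific, not total.

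**Conclusion.** The point holds as a contradiction that must be resolved before follow-up visits are booked. Depending on which passage a site follows, the untreated arm contributes 0 or up to 10 week-2 samples, taking 40 patients, equal quarters and full acceptance as the ceiling.

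Under 4.4, each drug versus no drug becomes inestimable, and pre/post change within an arm is confounded with visit-to-visit change. Contrasts among the three drug arms survive. The power figures assume d = 0.8 on the SD of change, and the drift figures are illustrative; the conclusion depends on neither. Aim 3 as written does not name the untreated arm under either reading. That is a separate gap in the analysis plan and could be closed later, whereas uncollected samples could not.

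**What to change.** Reconcile sections 4.4, 4.5.2, Table 1 and 4.5.6:

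- Reword 4.4 along these lines: week-2 follow-up (2 weeks +/- 4 days) is completed in all Group 1 participants who agree to the longitudinal component, including those allocated to no study drug.
- Show the no-drug arm in Table 1's longitudinal column, with the same follow-up blood and harvest.
- State in 4.5.6 that the longitudinal part includes that arm.

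The cost is protocol wording and at most 10 further visits, which the n = 40 row already implies. The downside is a second blood draw and harvest for untreated patients, which they may decline. Whether to follow patients who refuse the drug they are offered is a separate design choice and is not part of this change.

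If the sponsor does not intend untreated follow-up, the protocol should say so, and Aim 3 should limit any drug-versus-no-drug statement to uncontrolled pre/post description.
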